3.3.2 Inclusion criteria

Part A

1. Panretinal photocoagulation-treated DR patients with either no or inactive retinal neovascularization per investigator judgement in the study eye
2. Male or female subjects of age ≥ 18 years
3. Evidence of DMI per investigator's judgement, defined as any degree of disruption of retinal vascularity in OCTA
4. HbA1c of $\leq 12.0\%$
5. Best-corrected VA ≤ 75 letters (20/32) in the study eye
6. Best corrected VA in the non-study eye must be equal to or better than best corrected VA in the study eye. If both eyes are eligible (per inclusion #5) and have identical best corrected VA the investigator may select the study eye.
7. Women of childbearing potential (WOCBP) and men able to father a child must be ready and able to use two methods of contraception with at least one of them being a highly effective method of birth control per ICH M3 (R2) that result in a low failure rate of less than 1% per year when used consistently and correctly. A list of

contraception methods meeting these criteria is provided in the patient information in Section 4.2.2.3.

8. Signed and dated written informed consent in accordance with ICH GCP Harmonized Guideline for Good Clinical Practice and local legislation prior to admission to the trial

¹ A woman is considered of childbearing potential (WOCBP), i.e. fertile, following menarche and until becoming postmenopausal unless permanently sterile. Permanent sterilisation methods include hysterectomy, bilateral salpingectomy and bilateral oophorectomy. Tubal ligation is NOT a method of permanent sterilisation. A postmenopausal state is defined as no menses for 2 years without an alternative medical cause. A high follicle stimulating hormone (FSH) level in the postmenopausal range may be used to confirm a post-menopausal state in women not using hormonal contraception or hormonal replacement therapy. However, in the absence of 2 years of amenorrhoea, a single FSH measurement is insufficient.

Part B

1. Panretinal photocoagulation-treated DR patients with either no or inactive retinal neovascularization per investigator judgement
2. Male or female subjects of age ≥ 18 years
3. Presence of significant DMI: Large foveal avascular zone (FAZ) defined as those with $\geq 0.5\text{mm}^2$ area present on OCTA. If FAZ is $< 0.5\text{mm}^2$ then an enlarged peri-foveal inter-capillary space in at least 1 quadrant will be sufficient.
4. HbA1c of $\leq 12.0\%$

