7.5 RANDOMISATION

Part A

Subjects within a cohort receive the same trial medication, therefore no randomization for treatment assignment is performed.

Part B

Subjects will be randomized in a 2:1 ratio (BI 765128: Sham injection).

BI will arrange for the randomisation and the packaging and labelling of trial medication. The randomization list will be generated using a validated system, which involves a pseudo-random number generator so that the resulting treatment will be both reproducible and non-predictable. The block size will be documented in the Clinical Trial Report. Access to the codes will be controlled and documented.

The randomization list will contain additional blocks to allow for subject replacement (refer to Section [3.3.5](#)).

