7.6 DETERMINATION OF SAMPLE SIZE

Part A:

No formal statistical power calculations to determine sample size were performed for this explorative study. A Bayesian logistic regression model (BLRM) was used for guiding the dose escalation process (see Section [3.1](#) for details). For the SRD part, a minimum of 3 subjects and a maximum of 18 subjects will be expected for this trial based on the number of dose levels/cohorts that are tested (for details regarding the BLRM assumptions refer to appendix [10.3](#)). Fewer subjects might be needed based on the recommendation of the SMC. However, the actual number of subjects will depend on the number of dose cohorts tested. Based on the simulation study to evaluate operating characteristics of the BLRM, about 15 evaluable subjects are expected to be treated in the dose escalation part for the model to have reasonable operating characteristics relating to its MFD recommendation.

Part B:

In the publication Samara et al. [[R17-3318](#)] estimates for FAZ means and standard deviations (SD) were derived. The worst case was for PDR subjects with mean deep FAZ of 0.766 mm². The standard deviation of FAZ ranged from 0.112 mm² to 0.3402 mm² for disease categories from control to PDR. It is assumed that intra-individual variability is much lower than the inter-individual SD from Samara et al. because of the high correlation of the baseline and the FAZ values after treatment. Taking into account the high correlation, a SD of FAZ of 0.1 mm² seems to be reasonable to be used in calculation of risk probabilities. With 20 subjects in the BI 765128 [REDACTED] arm and 10 subjects in the sham arm, there is a likelihood of 81.7% of observing a treatment effect larger than 6% (a reduction of 0.0462 mm²) and a likelihood of 10.2% of observing a treatment effect smaller than 4% (a reduction of 0.0308mm²) when the assumed mean treatment difference is 10%. Assuming a mean treatment difference of 0% there is a likelihood of 12.3% observing a treatment effect larger than 6% and a likelihood of 78.7% of observing a treatment effect smaller than 4%.

8. INFORMED CONSENT, TRIAL RECORDS, DATA PROTECTION, PUBLICATION POLICY, AND ADMINISTRATIVE STRUCTURE

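### In Protocol 7.6 the stated 81.7% for Part B does not follow from its own inputs (they give 78.7%), and labelling the 0.766 mm² anchor the worst case is misleading when SD is 0.1 mm²

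*Protocol*

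**What the plan says.** Protocol 7.6 takes FAZ estimates from a cited OCTA publication: "The worst case was for PDR subjects with mean deep FAZ of 0.766" mm². It reports source SDs from 0.112 to 0.3402 mm² "for disease categories from control to PDR". It then replaces these with one smaller value: "Taking into account the high correlation, a SD of FAZ of 0.1" mm² "seems to be reasonable to be used in calculation of risk probabilities". No correlation coefficient is given.

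The group sizes are stated as "With 20 subjects in the BI 765128" arm and "10 subjects in the sham arm", which matches Protocol 7.5: "Subjects will be randomized in a 2:1 ratio (BI 765128: Sham injection").

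Four likelihoods follow:

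- True difference 10%: 81.7% for an observed effect above 6% (0.0462 mm²), and 10.2% for one below 4% (0.0308 mm²).
- True difference 0%: 12.3% for above 6%, and 78.7% for below 4%.

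No sensitivity to mean FAZ or SD is shown.

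Part B entry (Protocol 3.3.2, criterion 3) requires FAZ of at least 0.5 mm². For a smaller FAZ, "then an enlarged peri-foveal inter-capillary space in at least 1 quadrant will be sufficient". There is no upper limit. FAZ is analysed as change from baseline in mm² (Protocol 7.3.3; MMRM in SAP 7.5.2).

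**The concern.** Two things look wrong. First, the four likelihoods disagree with each other. With one SD, the distance from a true 10% to the 6% threshold equals the distance from a true 0% to the 4% threshold, so 81.7% and 78.7% cannot both be right. Second, a reader told that the anchor is the worst case will take the likelihoods as a floor on performance. With effects set as percentages and noise set in mm², a smaller FAZ means a smaller absolute effect against the same noise, so the anchor is not conservative for any smaller mean.

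At stake is how an observed FAZ difference is read. These likelihoods are the only quantitative support for the 30 subjects in Part B, and FAZ area is what the fast track analysis presents (SAP 7.5.3). If the chance of seeing more than 6% with no true effect is understated, a promising result would be over-read.

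**Working it through.** **Inputs (Protocol 7.6).** n = 20 and 10; SD = 0.1 mm². The base B follows from the converted thresholds: 0.0462/0.06 = 0.0308/0.04 = 0.77 mm² (0.766 rounded). The assumed effect is 0.10 × 0.77 = 0.077 mm².

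**Formula.** The observed mean difference is taken as Normal(δ, SE), with SE = SD × √(1/20 + 1/10) = 0.1 × 0.3873 = 0.03873 mm².

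**The plan's own figures.**

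- Above 6%, true 10%: Φ((0.077 − 0.0462)/0.03873) = Φ(0.795) = 78.7%. Stated 81.7%.
- Below 4%, true 10%: Φ((0.0308 − 0.077)/0.03873) = Φ(−1.193) = 11.6%. Stated 10.2%.
- Above 6%, true 0%: 1 − Φ(0.0462/0.03873) = 1 − Φ(1.193) = 11.6%. Stated 12.3%.
- Below 4%, true 0%: Φ(0.0308/0.03873) = Φ(0.795) = 78.7%. Stated 78.7%.

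The two tail figures are within 2 points of the stated values; 81.7% is 3.0 points too high. Rounding the base does not explain it (0.766 gives 78.6%), nor does a t distribution with 28 df (78.3%), a treated-arm SD of 0.09 (79.4%), or expressing the effect as a ratio to the observed sham mean (79.7%). An SD of 0.09 gives 81.2% but moves the other three values, to 9.3%, 9.3% and 81.2%. No variant tried reproduced all four. If the figures came from about 1,000 simulated trials, 81.7% would lie 2.3 standard errors from 78.7%, which is only marginally plausible. With 10,000 trials it would lie 7.4 away.

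**Sensitivity to mean FAZ and SD.** In general, P(>6% at true 10%) = P(<4% at true 0%) = Φ(0.04 B/SE), and P(>6% at true 0%) = P(<4% at true 10%) = 1 − Φ(0.06 B/SE).

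| Mean FAZ (mm²) | SD (mm²) | >6% at true 10% | >6% at true 0% |
|---|---|---|---|
| 0.40 | 0.10 | 66.0% | 26.8% |
| 0.50 | 0.10 | 69.7% | 21.9% |
| 0.60 | 0.10 | 73.2% | 17.6% |
| 0.77 | 0.10 | 78.7% | 11.6% |
| 0.90 | 0.10 | 82.4% | 8.2% |
| 0.77 | 0.15 | 70.2% | 21.3% |
| 0.50 | 0.0649 (= 0.1 × 0.5/0.77) | 78.7% | 11.6% |

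The last row shows that if SD is proportional to FAZ, the base drops out altogether.

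**What SD 0.1 implies.** For a change score, SD² = 2σ²(1 − ρ). Assuming the between-subject SD is the quoted maximum, σ = 0.3402: ρ = 1 − 0.01/(2 × 0.3402²) = 0.957. At ρ = 0.9 the change SD is 0.3402 × √0.2 = 0.152, close to the 0.15 row. With baseline adjustment, SD² = σ²(1 − ρ²) and the required ρ is 0.956, almost the same. At the other end of the quoted range, σ = 0.112, a change SD of 0.1 needs ρ of only 0.60.

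**The case against.** The strongest reply is that 0.5 mm² is an entry floor and not an expected mean, and that a floor raises the mean. As an illustration, assume FAZ is normal around 0.766 mm². Truncating below 0.5 mm² gives a mean of 0.769 (SD 0.112) to 0.894 (SD 0.3402), and hence 78.6% to 82.2% for seeing more than 6% at a true 10%. Admitting everyone below 0.5 mm² by the inter-capillary route would only bring the mean back to 0.766. PDR is also a natural anchor, since Part B enrols PRP-treated patients. In addition, 0.766 is a deep-plexus value, while the Part B entry criterion names no plexus, so the two numbers may not be directly comparable.

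This reply stands against a stronger reading that a reader might infer: that 0.766 is the most favourable case and that the likelihoods fail for the population enrolled. The documents do not support that. They give no mean for other disease categories, no expected mean for Part B, and no rule for how SD behaves at other FAZ sizes. The worst-case label may simply mean the most severe disease.

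The reply does not rescue the 81.7%, which fails at the plan's own base and SD. Nor does it make the anchor conservative for a smaller mean at SD 0.1 mm².

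It is also fair that the consequence is small. Part B's primary endpoint is drug-related AEs, FAZ is secondary, Protocol 7.2 rules out confirmatory testing, and the documents do not make 6% or 4% a decision rule.

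**Conclusion.** The point holds, as a minor one. At the plan's own inputs the four likelihoods are 78.7%, 11.6%, 11.6% and 78.7%. The stated 81.7% is 3.0 points too high and contradicts the stated 78.7%. The tails move by 1.4 points (10.2%) and 0.7 points (12.3%); the second correction is in the plan's favour.

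The worst-case label is misleading for these likelihoods, but a shortfall from the anchor is conditional. It needs an enrolled mean FAZ clearly below 0.77 mm² and an SD that does not shrink with FAZ. If the mean were 0.5 mm² with SD 0.1 mm², the chance of seeing more than 6% at a true 10% would be 69.7%. Of the 12.0 points below 81.7%, 3.0 come from the figure that does not reproduce and 9.0 from the anchor. The false-signal chance would be 21.9% against the stated 12.3%. A mean above 0.77 mm² would improve both.

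The SD matters at least as much: 0.15 mm² at the plan's own base gives 70.2% and 21.3%. All of this rests on a normal approximation with a common SD in both arms.

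**What to change.** In Protocol 7.6:

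1. Correct 81.7% to 78.7% and both tail figures to 11.6%, or state the simulation method and number of runs that produced the stated values.
2. Delete the worst-case label, or say in what sense it is meant.
3. Tabulate the four likelihoods over mean FAZ of about 0.4 to 0.9 mm² and SD of 0.1 to 0.15 mm², so that the range extends both below and above the anchor. State whether SD is assumed constant or proportional to FAZ, and give the baseline/post-treatment correlation behind the 0.1 mm².

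Keep 20 versus 10. The cost is protocol text only; no analysis or sample size changes. The downside is that the headline likelihood becomes slightly less favourable and the table shows weaker cases openly.

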4.1.3 Method of assigning subjects to treatment groups

After the assessment of all in- and exclusion criteria, subjects will be enrolled into the Part A and Part B. Recruitment in the trial will start with the lowest dose group of Part A. Part B will recruit subjects only after Part A has been completed and safety of the doses has been established.

In Part A, the dose is planned to be escalated in cohorts at the pre-defined provisional dose levels; see Table 4.1.2: 1. Intermediate or lower dose levels, depending on the number of DLEs observed in the study, as long as they fulfil the EWOC criterion, may be investigated if agreed upon between Investigator and Sponsor. At the end of each treatment cohort, BI will convene a meeting with the SMC members. At the dose escalation meeting, all available systemic and ophthalmological safety data (See section 3.1 and 5.2.1) will be reviewed in

detail. Based on that and on the results of the updated BLRM, a decision on the next dose level to be tested is made.

In general, recruitment for Part A will be done successively for the dose groups, i.e. if the required number of subjects for one dose group is completed and this dose is considered safe based on (the BLRM model and the clinical course), the recruitment of the next higher dose group may be started. Therefore, the recruitment of subjects for the dose groups will neither be influenced by the trial personnel nor by any characteristics of the subjects, but only by temporal availability. Subjects from the Part A are not allowed to participate in Part B.

The highest dose (██████), if established as safe and tolerable during Part A will be used in Part B after Part A has been completed. If the highest dose (██████) is not considered safe and tolerable Part B will not commence. In Part B subjects will be randomized to receive either active IVT treatment or sham injection according to a randomization plan at visit 2 via Interactive Response Technology (IRT). 20 subjects will receive IVT treatment and 10 will receive sham injection.

The randomization procedure is described in Section [7.5](#).

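### The Part B likelihoods in Protocol 7.6 do not follow from the stated SD and arm sizes: 81.7% should be 78.7%, and the four figures are mutually inconsistent

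*Protocol*

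**What the plan says.** Protocol 7.6 (Part B) takes its reference value from a published study: "The worst case was for PDR subjects with mean deep FAZ of 0.766 mm²". It argues that variability within a subject is much lower than the between-subject SDs in that study, and concludes that "a SD of FAZ of 0.1 mm² seems to be reasonable to be used in calculation of risk probabilities". The arm sizes are 20 in the active "arm and 10 subjects in the sham arm"; section 4.1.3 agrees ("20 subjects will receive IVT treatment and 10 will receive sham injection").

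Four likelihoods follow, with cut-offs of 6% (0.0462 mm²) and 4% (0.0308 mm²):

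- True difference 10%: "there is a likelihood of 81.7% of observing a treatment effect larger than 6" per cent, and "a likelihood of 10.2% of observing a treatment effect smaller than 4" per cent.
- True difference 0%: 12.3% for an effect above 6%, and "a likelihood of 78.7% of observing a treatment effect smaller than 4" per cent.

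For Part B, section 7.6 mentions no other SD, no simulation and no other method. Section 7.2 says there is no confirmatory testing and refers to 7.6 for the discussion of sample size.

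**The concern.** The 6% cut-off lies four percentage points below a true 10%. The 4% cut-off lies four percentage points above a true 0%. With one SD and a symmetric distribution of the observed difference, the chance of exceeding 6% when the truth is 10% must equal the chance of falling below 4% when the truth is 0%. The protocol prints 81.7% and 78.7%. In the same way, the chance of falling below 4% under 10% must equal the chance of exceeding 6% under 0%, yet these are printed as 10.2% and 12.3%. The contradiction is visible before any SD is used.

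Because no hypothesis is tested, these four figures are the only quantitative support for the Part B size. They tell the reader how often a 20 + 10 comparison would point the right or the wrong way on FAZ. FAZ is a secondary endpoint, and its area is what the fast track analysis presents (SAP 7.5.3).

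**Working it through.** **Inputs, all from Protocol 7.6**

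- SD = 0.1 mm², common to both arms
- n = 20 active, 10 sham
- Cut-offs 0.0462 and 0.0308 mm². These imply a base of 0.77 mm² (0.0462/0.06 = 0.0308/0.04 = 0.77), which is 0.766 rounded.
- True difference 10% of 0.77 = 0.077 mm², or 0

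**Standard error of the difference**

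SE = 0.1 × √(1/20 + 1/10) = 0.1 × √0.15 = 0.03873 mm²

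**Likelihoods, normal distribution of the difference in means**

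The figure that reproduces comes first.

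| Quantity | Calculation | Result | Printed |
|---|---|---|---|
| Below 4%, truth 0% | Φ(0.0308/0.03873) = Φ(0.795) | 78.7% | 78.7% |
| Above 6%, truth 10% | Φ((0.077 − 0.0462)/0.03873) = Φ(0.795) | 78.7% | 81.7% |
| Below 4%, truth 10% | Φ((0.0308 − 0.077)/0.03873) = Φ(−1.193) | 11.6% | 10.2% |
| Above 6%, truth 0% | 1 − Φ(0.0462/0.03873) = 1 − Φ(1.193) | 11.6% | 12.3% |

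The first two rows use the same distance (0.0308 mm²) and the same SE, so they cannot differ.

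**SD implied by each printed figure**

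SD = distance / (|z| × √0.15), where z is the normal quantile of the printed likelihood:

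- 81.7%: 0.0308/(0.904 × 0.3873) = 0.088 mm²
- 10.2%: 0.0462/(1.270 × 0.3873) = 0.094 mm²
- 12.3%: 0.0462/(1.160 × 0.3873) = 0.103 mm²
- 78.7%: 0.0308/(0.796 × 0.3873) = 0.100 mm²

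**Variants that do not close the gap**

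Results are in the protocol's order: above 6% and below 4% at a true 10%, then above 6% and below 4% at a true 0%.

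- Base 0.766 throughout: 78.6, 11.8, 11.8, 78.6
- t distribution, 28 df: 78.3, 12.1, 12.1, 78.3
- SD 0.095 instead of 0.1 (best single compromise): 79.9, 10.5, 10.5, 79.9
- Active-arm SD also reduced by 10% when the effect is present: 79.4, 10.9, 11.6, 78.7
- Other arm sizes (15:15, 20:20, 10:10, 24:12, 26:13): each gives equal pairs, so none can match

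**The case against.** Section 7.6 does not say how the likelihoods were calculated, so the normal closed form is an inference. Two ordinary alternatives come near the printed values.

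*Simulation.* The Part A operating characteristics in Appendix 10.3 used 1000 simulated trials per scenario. With 1000 runs, 81.7% lies 2.3 standard errors from 78.7%. Tested jointly, the four printed figures give a chi-square of 6.4 on 4 df (p = 0.17), so simulation noise at that run count is not excluded. By 2000 runs it no longer explains the figures (p = 0.013).

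*Percentage scale.* A log-ratio calculation with CV = 0.1/0.77 gives 80.6, 10.0, 10.9 and 79.1. A ratio of means with the active-arm SD also cut by 10% gives 80.5, 10.2, 10.7 and 79.3. Both produce unequal pairs in the printed direction, and all values are within 2 points of the printed ones.

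Neither rescues the text. If noise is the cause, the quantity being estimated is still 78.7%. Neither percentage-scale model gives all four printed figures. Section 7.6 describes neither method for Part B; it gives one SD in mm² and cut-offs in mm².

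The limits on importance do stand. One figure is exact, two are within 1.4 points of the computed value, and only 81.7% is off by as much as 3 points. The printed 12.3% is less favourable to the design than the computed 11.6%. FAZ is a secondary endpoint in an exploratory trial, and section 7.6 does not call 6% or 4% decision thresholds. The arm sizes and the analysis model do not depend on these figures.

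**Conclusion.** The point holds. Under the stated SD, arm sizes and cut-offs, with a normal distribution for the difference in means, the likelihoods are 78.7%, 11.6%, 11.6% and 78.7%. The printed 81.7% is 3.0 points too high, 10.2% is 1.4 points too low and 12.3% is 0.7 points too high. The inconsistency between the pairs needs less: only one SD, absolute cut-offs and a symmetric distribution. The effect on the design is small, but these are wrong stated figures in the paragraph that justifies the Part B size.

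Separately, and not as a second error, all four values are sensitive to the SD, which the protocol openly presents as an assumption. If 0.1 mm² is the SD of the change and the quoted 0.3402 mm² applies both before and after treatment, the required correlation is 1 − 0.1²/(2 × 0.3402²) = 0.957. At an assumed correlation of 0.90 the SD is 0.3402 × √0.2 = 0.152 mm² and the SE is 0.0589 mm². The chance of observing more than 6% is then about 70% when the truth is 10% and about 22% when the truth is 0%.

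**What to change.** In Protocol 7.6, replace the four likelihoods with 78.7% and 11.6% (true difference 10%) and 11.6% and 78.7% (true difference 0%), and add one sentence saying that they assume a normal distribution for the difference in means with a common SD of 0.1 mm². If a different model or a simulation produced the printed figures, describe it instead, including the scale and any number of runs, and make it agree with the stated SD. Keep 20 + 10.

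The cost is one corrected paragraph and a leading figure 3 points less favourable. No subjects, visits or analyses are added.

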8.1 TRIAL APPROVAL, PATIENT INFORMATION, INFORMED CONSENT

This trial will be initiated only after all required legal documentation has been reviewed and approved by the respective Institutional Review Board (IRB / Independent Ethics Committee (IEC and competent authority (CA) according to national and international regulations. The same applies for the implementation of changes introduced by amendments.

Prior to subject participation in the trial, written informed consent must be obtained from each subject (or the subject’s legally accepted representative) according to ICH-GCP and to the regulatory and legal requirements of the participating country. Each signature must be personally dated by each signatory and the informed consent and any additional patient-information form retained by the investigator as part of the trial records. A signed copy of the informed consent and any additional subject information must be given to each subject or the subject’s legally accepted representative.”

The subject must be given sufficient time to consider participation in the trial. The investigator or delegate obtains written consent of the subject’s own free will with the informed consent form after confirming that the subject understands the contents. The investigator or [REDACTED] delegate must sign (or place a seal on) and date the informed consent form. If a trial collaborator has given a supplementary explanation, the trial collaborator also signs (or places a seal on) and dates the informed consent.

Re-consenting may become necessary when new relevant information becomes available and should be conducted according to the sponsor’s instructions.

The consent and re-consenting process should be properly documented in the source documentation.

